7.5. Adverse Event Reporting

Adverse Event Definitions

Adverse event. Any untoward medical occurrence in a clinical study; regardless of the causal relationship of the event with the investigational drug or study treatment(s).

Associated with the use of the investigational drug or study treatment(s). There is a reasonable possibility that the adverse event may have been caused by the investigational drug or study treatment(s).

Disability. A substantial disruption of a person's ability to conduct normal life functions.

Life-threatening adverse event. Any adverse event that places the participant, in the view of the investigator, at immediate risk of death from the event as it occurred (i.e., does not include an adverse event that, had it actually occurred in a more severe form, might have caused death).

Serious adverse event. SAEs will be defined as any adverse experience that is unexpected or: i) results in death; ii) results in persistent or significant disability/incapacity; iii) results in or prolongs an existing inpatient hospitalization (even if the hospitalization is a precautionary measure for observation); iv) is a congenital anomaly/birth defect in offspring of subjects taking the product regardless of time to diagnosis; v) is the result of an overdose, whether accidental or intentional; or vi) is a suicide attempt (but not suicidal ideation).

Hospitalization shall include any initial admission (even if less than 24 hours) to a healthcare facility as a result of a precipitating clinical adverse event; to include transfer within the hospital to an intensive care unit. Hospitalization or prolongation of hospitalization in the absence of a precipitating, clinical adverse event (e.g. for a preexisting condition not associated with a new adverse event or with a worsening of the preexisting condition; admission for a protocol-specified procedure) is not, in itself, a serious adverse event.

Unexpected adverse event. Any adverse event, the frequency, specificity or severity of which is not consistent with the risk information described in the clinical protocol(s) or elsewhere in the current IND application, as amended.

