7.4. Data and Safety Monitoring Board (DSMB)

The MPRC has established a Data and Safety Monitoring Board (DSMB), which is comprised of two psychiatrists, a statistician, a pharmacist, and a community representative. The psychiatrists are experts in the clinical treatment of people with schizophrenia. None of the DSMB members reviewing this study will be investigators on the proposed project; however, [name] serves as a non-voting member of the DSMB to assist in the monitoring of all MPRC trials. The DSMB will be charged with the following responsibilities: 1) to review the proposed protocol; 2) to monitor study progress and the occurrence of side effects/adverse events, and serious adverse events throughout the course of the study; and 3) to review with [name], the statistician for the project, the study data management system. The DSMB will review reports on protocol progress, side effects and adverse events at least once a year. In addition, all serious adverse events (SAEs) will be reported to the DSMB, [name], and the University of Maryland School of Medicine IRB. [name] will receive all SAE reports within 24 hours of their occurrence. The DSMB and University of Maryland School of Medicine IRB will receive the reports within 48 hours. If the incidence of any side effect/adverse event is 25% or more or any SAE occurs in excess in either treatment group, then the DSMB will notify the P.I.s. The P.I.s and DSMB will determine whether possible protocol modifications are required to minimize the further occurrence of such events.

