7.10. Telephoned IND Safety Reports

In addition to the subsequent submission of a written IND Safety Report (i.e., completed FDA Form 3500A), the investigator-sponsor will notify the responsible review division of the FDA by telephone or facsimile transmission of any observed or volunteered adverse event that is 1) associated with the use of the investigational drug or study treatment(s); 2 fatal or life-threatening; and 3) unexpected.

The telephone or facsimile transmission of applicable IND Safety Reports will be made as soon as possible but in no event later than 7 calendar days after the investigator-sponsor's initial receipt of the respective human adverse event information.

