7.11. Reporting Adverse Events to the Responsible IRB

In accordance with applicable policies of UCLA and the University of Maryland Institutional Review Boards (IRB's), the investigator will report, to the IRB, any observed or volunteered adverse event that is determined to be 1) associated with the investigational drug or study treatment(s); 2) serious; and 3) unexpected. Adverse event reports will be submitted to the IRB in accordance with the respective IRB procedures.

Applicable adverse events will be reported to the IRB as soon as possible and, in no event, later than 10 calendar days following the investigator's receipt of the respective information.

Adverse events which are 1) associated with the investigational drug or study treatment(s); 2) fatal or life-threatening; and 3) unexpected will be reported to the IRB within 24 hours of the investigator's receipt of the respective information.

Follow-up information to reported adverse event will be submitted to the IRB as soon as the relevant information is available. If the results of the investigator's follow-up investigation show that an adverse event that was initially determined to not require reporting to the IRB does, in fact, meet the requirements for reporting; the investigator will report the adverse event to the IRB as soon as possible, but in no event later than 10 calendar days, after the determination was made.

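### The SAE definition in 7.5 omits life-threatening events, so an expected one meeting none of criteria i–vi is not an SAE and misses the 48-hour DSMB report

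*Combined protocol and SAP*

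**What the plan says.** Section 7.5 (Adverse Event Reporting) defines the term: "Life-threatening adverse event. Any adverse event that places the participant, in the view of the investigator, at immediate risk of death". The SAE definition follows in the next paragraph. It begins "SAEs will be defined as any adverse experience that is unexpected or: i) results in death; ii) results in persistent or significant disability/incapacity" and goes on "iii) results in or prolongs an existing inpatient hospitalization (even if the hospitalization is a precautionary measure for observation", then "iv) is a congenital anomaly/birth defect in offspring of subjects taking the product regardless of time to diagnosis", and ends "v) is the result of an overdose, whether accidental or intentional; or vi) is a suicide attempt (but not suicidal ideation". The list runs unbroken from i to vi. It has no life-threatening criterion and no general clause for other medically important events.

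Section 7.4 ties fast reporting to SAE status: "all serious adverse events (SAEs) will be reported to the DSMB". The DSMB and the University of Maryland IRB receive those reports within 48 hours. The DSMB also notifies the principal investigators if SAEs occur in excess in either arm. Side effects and adverse events in general go to the DSMB in reports at least once a year.

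Life-threatening events have an operational role in two other places. Section 7.10 asks for a telephone or fax report to the FDA when an event is related and also "2 fatal or life-threatening; and 3) unexpected". Section 7.11 says that related events that are fatal or life-threatening and "unexpected will be reported to the IRB within 24 hours". Neither section names the DSMB as a recipient.

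**The concern.** A term defined in 7.5 and paired with fatal events in 7.10 and 7.11 would be expected among the criteria for seriousness. Death is on the list and immediate risk of death is not. SAE status decides whether the DSMB hears of an event within 48 hours and whether the event counts when SAEs are compared between arms. An event outside the definition loses both. Meanwhile a trivial but unexpected event qualifies for both, because being unexpected is enough. The DSMB's SAE comparison could thus include a minor event and leave out one that put a participant at immediate risk of death.

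**Working it through.** The plan gives no figure to reproduce, so the check is a logical one.

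**Step 1. The rule.** Read literally, 7.5 says: SAE = unexpected, or (i) death, or (ii) disability or incapacity, or (iii) hospitalization, or (iv) birth defect, or (v) overdose, or (vi) suicide attempt.

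**Step 2. Apply it to a life-threatening event.**

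| Life-threatening event | Limb of 7.5 met | SAE? | Route to the DSMB under 7.4 |
|---|---|---|---|
| Meets any of i–vi | that criterion | Yes | 48 hours |
| Meets none of i–vi, unexpected | the opening limb | Yes | 48 hours |
| Meets none of i–vi, expected | none | **No** | Adverse-event reports, at least yearly |

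Only the third row is a gap.

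**Step 3. Does another section close it?**

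- 7.9 (written IND report) requires the event to be associated with treatment, serious and unexpected. An expected event is outside it.
- 7.10 and 7.11 (7 days to the FDA, 24 hours to the IRB) require association and unexpectedness. An expected event is outside both.
- 7.6 and 7.8 require the event to be recorded and promptly reviewed by the investigator-sponsor. Seriousness is then judged against the same 7.5 list, so the answer does not change.

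**Step 4. What the DSMB would still act on.** For events that are not SAEs, the notification trigger in 7.4 is an incidence of 25% or more. Section 8.6 plans 33 participants per arm. At full enrolment the trigger needs 0.25 × 33 = 8.25, that is 9 participants, if read per arm. Read over the whole trial it needs 0.25 × 66 = 16.5, that is 17. For SAEs the trigger is any excess, with no minimum count. An event in the third row is thus moved from the sensitive trigger to one that a handful of events cannot reach.

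**Step 5. Dependence on the opening limb.** The second row counts as serious only because 7.5 treats unexpectedness as sufficient. That sits badly with 7.9 and 7.11, which list serious and unexpected as separate conditions; under 7.5 as written, the first adds nothing to the second. If that limb were removed and nothing added, the second row would join the third, and every life-threatening event outside i–vi would lose SAE status. This describes a possible amendment, not the present plan.

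**The case against.** The strongest reply is that the gap is small and may be empty. An event must be life-threatening, expected, and outside all six criteria. Criterion iii is broad: it covers precautionary observation, and 7.5 counts admissions of under 24 hours. Disability, overdose and suicide attempt qualify without admission. An event is also unexpected under 7.5 if its severity is out of line with the stated risk information. The documents list no expected life-threatening risk, so life-threatening severity would often make an event unexpected and hence serious. Section 11.4 does not anticipate stopping the study for safety. All of this stands, and it limits the size of the point. It does not remove it: the IND may describe such risks, and the definition should not depend on whether it does.

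A reader might also infer three stronger things that the documents do not support.

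- *Any life-threatening event without admission escapes the DSMB as an SAE.* It does not; the opening limb of 7.5 captures every unexpected one.
- *Reports to the FDA or IRB under 7.9 to 7.11 would be missed or left without a footing.* They would not. Each of those rules applies only to unexpected events, which 7.5 already makes serious. The pairing of fatal with life-threatening in 7.10 and 7.11 shows what the authors regarded as grave, but it does not show a failed report.
- *The 24-hour IRB clock in 7.11 and the 48-hour DSMB clock in 7.4 contradict each other.* Different deadlines for different bodies and classes of event are not a contradiction. Tying the DSMB clock to 7.11 would not help either, because 7.11 does not reach expected events.

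**Conclusion.** The omission is certain on the text: 7.5 defines the term, leaves it off the SAE list, and no other section adds it. The consequence is confined to expected life-threatening events meeting none of criteria i–vi. These miss the 48-hour DSMB report and the SAE-excess comparison. They are not lost altogether: they are recorded, reviewed by the investigator-sponsor, included in the DSMB's adverse-event review at least yearly, and tabulated under 8.5.

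Their number cannot be derived, since the documents give neither a list of expected risks nor an SAE rate. If SAE counts are small, which is an assumption but a plausible one with 33 per arm, a single classification could decide whether an excess is seen. The conclusion rests on a literal reading of 7.5 and on the sections available; the IND is not among them. This is a definitional correction to a safety rule, worth making because it is simple and because the wording that now limits the gap is itself open to correction.

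**What to change.** Add one criterion to the SAE list in 7.5: *is life-threatening (as defined above)*. This by itself brings the affected events under the existing 48-hour rule and the SAE comparison in 7.4, so neither 7.4 nor the reporting clocks need to change.

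If the sponsor also revises the opening limb so that unexpectedness alone no longer makes an event serious, both edits should go into the same amendment, and 7.5 should be read against 7.9 to 7.11 so that the two terms are used consistently.

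The cost is one line in 7.5 and a matching tick-box on the case report form. No visits, participants or procedures are added.

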7.6. Recording Requirements

All observed or volunteered adverse drug events (serious or non-serious) and abnormal test findings, regardless of treatment group or suspected causal relationship to the investigational drug or study treatment(s) will be recorded in the participants' case record forms. For all adverse events, sufficient information will be pursued and/or obtained so as to permit 1) an adequate determination of the outcome of the event (i.e., whether the event should be classified as a serious adverse event) and; 2) an assessment of the causal relationship between the adverse event and the investigational drug or study treatment(s).

Adverse events or abnormal test findings felt to be associated with the investigational drug or study treatment(s) will be followed until the event (or its sequelae) or the abnormal test finding

resolves or stabilizes at a level acceptable to the investigator-sponsor (or, if applicable, the medical or dental director for the investigator-sponsor).

7.7. Abnormal Test Findings

An abnormal test finding will be classified as an adverse event if one or more of the following criteria are met:

The test finding is accompanied by clinical symptoms and of clinical significance.

The test finding necessitates additional diagnostic evaluation(s) or medical/surgical intervention; including significant additional concomitant drug treatment or other therapy. Note: simply repeating a test finding, in the absence of any of the other listed criteria, does not constitute an adverse event.

The test finding leads to a change in study dosing or discontinuation of subject participation in the clinical study.

The test finding is considered an adverse event by the investigator-sponsor of the IND application.

7.8. Causality and Severity Assessment

The investigator-sponsor of the IND application will promptly review documented adverse events and abnormal test findings to determine 1) if the abnormal test finding should be classified as an adverse event; 2) if there is a reasonable possibility that the adverse event was caused by the investigational drug or study treatment(s); and 3) if the adverse event meets the criteria for a serious adverse event.

If the investigator-sponsor's final determination of causality is "unknown and of questionable relationship to the investigational drug or study treatment(s)", the adverse event will be classified as associated with the use of the investigational drug or study treatment(s) for reporting purposes. If the investigator-sponsor's final determination of causality is "unknown but not related to the investigational drug or study treatment(s)", this determination and the rationale for the determination will be documented in the respective subject's case history.

7.9. Written IND Safety Reports

The investigator-sponsor will submit a written IND Safety Report (i.e., completed FDA Form 3500 A) to the responsible new drug review division of the FDA for any observed or volunteered adverse event that is determined to be 1) associated with the investigational drug or study treatment(s); 2) serious; and 3) unexpected. Each IND Safety Report will be prominently labeled, "IND Safety Report", and a copy will be provided to all participating sub-investigators.

Written IND Safety Reports will be submitted to the FDA as soon as possible and, in no event, later than 15 calendar days following the investigator-sponsor's receipt of the respective adverse event information.

For each written IND Safety Report, the sponsor-investigator will identify all previously submitted IND Safety Reports that addressed a similar adverse event experience and will provide an analysis of the significance of newly reported adverse event in light of the previous, similar report(s).

Follow-up information to an IND Safety Report will be submitted to the applicable review division of the FDA as soon as the relevant information is available. If the results of the sponsor-investigator's follow-up investigation show that an adverse event that was initially determined to not require a written IND Safety Report does, in fact, meet the requirements for reporting; the investigator-sponsor will submit a written IND Safety Report as soon as possible, but in no event later than 15 calendar days, after the determination was made.

7.10. Telephoned IND Safety Reports

In addition to the subsequent submission of a written IND Safety Report (i.e., completed FDA Form 3500A), the investigator-sponsor will notify the responsible review division of the FDA by telephone or facsimile transmission of any observed or volunteered adverse event that is 1) associated with the use of the investigational drug or study treatment(s); 2 fatal or life-threatening; and 3) unexpected.

The telephone or facsimile transmission of applicable IND Safety Reports will be made as soon as possible but in no event later than 7 calendar days after the investigator-sponsor's initial receipt of the respective human adverse event information.

7.11. Reporting Adverse Events to the Responsible IRB

In accordance with applicable policies of UCLA and the University of Maryland Institutional Review Boards (IRB's), the investigator will report, to the IRB, any observed or volunteered adverse event that is determined to be 1) associated with the investigational drug or study treatment(s); 2) serious; and 3) unexpected. Adverse event reports will be submitted to the IRB in accordance with the respective IRB procedures.

Applicable adverse events will be reported to the IRB as soon as possible and, in no event, later than 10 calendar days following the investigator's receipt of the respective information.

Adverse events which are 1) associated with the investigational drug or study treatment(s); 2) fatal or life-threatening; and 3) unexpected will be reported to the IRB within 24 hours of the investigator's receipt of the respective information.

Follow-up information to reported adverse event will be submitted to the IRB as soon as the relevant information is available. If the results of the investigator's follow-up investigation show that an adverse event that was initially determined to not require reporting to the IRB does, in fact, meet the requirements for reporting; the investigator will report the adverse event to the IRB as soon as possible, but in no event later than 10 calendar days, after the determination was made.

7.12. Withdrawal of Participants Due to Adverse Events

If unanticipated and serious adverse events emerge and are considered related or possibly related to study drug, the study may be stopped and all currently participating participants will be contacted to stop taking the study drugs and complete any final study procedures (safety associated laboratory test, etc). The respective IRBs and FDA will be notified of such actions by the investigators at each site, and by the IND holder at Pittsburgh to the FDA.

Similarly, if the holder of the CTD, Natreon, Inc informs the IND holder or the PI/Co-I of unanticipated adverse events that have emerged and could place currently enrolled participants at greater risk for physical and psychological harm than anticipated then actions for stopping the study and follow-up as described above will be initiated by the PI and research staff in conjunction with the IND holder and other responsible entities (e.g. FDA).

8. Statistical Methods/Data Analysis

8.1 Primary Endpoint(s)

For *Specific Aim 1*, an intention-to-treat strategy will be used for analysis and participants will be analyzed as part of the group to which they were randomized. A linear mixed model will be used to examine changes in measures of psychopathology (PANSS Total, Positive and Negative Symptoms and General Psychopathology Subscales) and psychosocial stress (PSS). For the primary endpoint (PANSS Total Score), a model that includes visit, treatment, visit * treatment interaction as fixed effects with baseline PANSS total score as a covariate will be used. Model-estimated marginal means for scheduled

visits will be computed per treatment group to examine time to response. Linear mixed models use all available data, account for non-independence of repeated measures and provide unbiased estimates if missing data are present.

8.3. Definition(s): Analysis population(s)

Any participant who provides informed consent and completes screening procedures, and receives randomized study medication, and also comes in for at least one additional study visit will form the safety population for data analyses.

Any participant who was randomized and provided baseline plus at least one other visit where the PANSS and PSS scales assessments were reassessed will form the intent to treat population for efficacy analyses for the primary outcomes.

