3.3 Recruitment Targets and Timelines

3.4 Schedule of Events

Approximate Visit Intervals	V1	V2	V3	V4	V5	V6	V7	V8
				2 wks	4 wks	6 wks	8 wks	10 wks
Informed Consent, Urine Drug Test, Pregnancy test, Psychiatric		X						
Diagnosis and History, Medical History								
Labs, EKG ¹		X						X
PANSS, CGI, PSS ²	X	X	X	X		X		X
MCCB		X				X		X
BP, Pulse, Temperature Weight, Height ³	X	X	X	X	X	X	X	X
Sensoril or Placebo		X	X	X	X	X	X	X
Treatment Emergent Adverse Events or Serious Adverse Events			X	X	X	X	X	X

Visit Comments, Pill Counts ⁴	X	X	X	X	X	X	X	X
--	---	---	---	---	---	---	---	---

Visit 1 can be split up (if needed) into 2 visits for screening and spread over 1 to 4 weeks. Visit 2 is the randomization visit. Following randomization, visit intervals for V3 through V8 can range from \pm 4 days of the expected between interval visits; exceptions on a case by case basis by the study team.

Visits 1 and 8 will last roughly 2 hours. Visits 2, 3, 4, 5, 6, and 7 will last roughly 1 hour.

At Visit 1 – Urine drug test for illicit substances will occur as will a serum pregnancy test for women in the reproductive age group.

¹Labs: CBC + Diff, Chemistry 14? (including liver and renal functions, electrolytes, blood sugar, and lipid profile), urine analysis, and hs CRP and serum for cytokine panels

¹EKG: standard EKG

² The Positive and Negative Syndrome Scale (PANSS), Clinical Global Impression Scale (CGI), Perceived Stress Scale (PSS),

³ Height at screening only, waist circumference and BMI at screening and visit 8 or end of study.

⁴ Pill Counts – will start at visit 3, i.e., post randomization

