7.2. Study Treatments, Assessments and Follow up

After all screening procedures have been completed and reviewed and the participant remains eligible for the study, the participant will receive either Sensoril® or placebo at visit 2. The

participant will get one of these medicines by chance (like flipping a coin), and have a 1 in 2 chance of getting either Sensoril® or placebo. The medicine is packaged identically so that it is not possible to tell which is Sensoril® or which is placebo. The medicine will be given to the participant as capsules, and is taken by mouth. Starting at 1 capsule twice daily, the medicine (or placebo) will be increased to 2 capsules twice daily a week later, unless the participant is experiencing side effects. Neither the participant, or the doctor or the research staff will know if the participant is receiving Sensoril® or placebo.

If any tolerability issues emerge, further titration of study medicines can be stopped at a minimum 500 mg/day. If dosage has been increased to 1000 mg/day it can be decreased to 500 mg/day for side-effects.

Details of procedures at each visit (Visit 1 to 8) are described in the schedule of events (**3.2.c.**). Psychopathology ratings (details of the scales were described in **Section 3.2.d** earlier) are briefly mentioned in section 7.1.a. Safety assessments will include determination of side effects at each visit, and depending on the side effects, further clinical action will be undertaken. Laboratory measures at baseline and end point will provide more safety data as will careful monitoring of physical and psychological status at each visit.

If the participant would like to know the treatment assignment at the end of the data analyses and if a contact address or phone number is left with research staff, we will attempt to notify them of their treatment assignment during the study.

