8.5. Safety Analysis

Safety analyses of vital signs, laboratory measures, body weight etc. will be evaluated for the safety population, either as continuous or categorical variables (for instance – normal, abnormal etc). Further, the treatment-emergent adverse events will be grouped by organ-system and tabulated by treatment assignment, and rates between treatments will be compared using contingency statistics (chi-square or other Fishers Exact test) for categorical variables and T-tests for continuous variables.

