11.3 Investigator-Sponsor Discontinuation Criteria

Criteria and procedures for terminating the participation of an individual study subject

A research subject will be terminated from study participation in the event that:

1. Subject fails to follow-up with study procedures and study visits despite reasonable efforts on the part of the research staff to contact him/her will be discontinued from the study.
2. Subject experiences a serious adverse event that is unanticipated and thought to be possibly related to study drug will be discontinued from the study.
3. An unanticipated and serious adverse event emerges and is considered related or possibly related to study drug, the study may be stopped and all currently participating subjects contacted to stop taking the study drugs and complete any final study procedures (safety associated laboratory test, etc). The DSMB, IRB and FDA will be notified on such actions.
4. A female subject becomes pregnant during study participation.

Note: Missing multiple doses of study treatment does not qualify as a reason for termination. Participants who miss multiple doses will be encouraged to resume study medication at the standard BID schedule. However, if it is determined that a participant's study drug treatment has been interrupted for greater than 7 consecutive days, that individual may be considered for removal from the study by the investigator-sponsor.

Termination procedures:

- Perform a final on-site or telephone assessment of adverse event occurrence.
- Request the return of any remaining study drug doses. If necessary, send a pre-paid envelope to the participant and include a request that the participant return the study drug as soon as possible.
- Complete study drug accountability record to account for any returned doses and the subsequent disposal of such doses in accordance with guidelines of the Investigational Drug Service

Subjects withdrawn due to a serious unexpected adverse event will only be replaced once full assessment of the event has taken place, in order to ensure the safety of additional subjects. Replacements will occur in this study only up to the limits allowed by availability of subjects' budget considerations.

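### The safety population leaves out treated participants who never come back, even if an adverse event was recorded; separately, 7.5 classes every unexpected event as serious

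*Combined protocol and SAP*

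**What the plan says.** **Safety population.** Section 7.2 states that "the participant will receive either Sensoril® or placebo at visit 2". Section 8.3 requires consent, completed screening and receipt of drug, and then attendance: the participant "receives randomized study medication, and also comes in for at least one additional study visit will form the safety population for data analyses". No other safety set is defined.

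**Recording of events.** Section 7.6 requires observed and volunteered events to go into the case record form and sets no attendance condition. When participation ends, 11.3 tells staff to "Perform a final on-site or telephone assessment of adverse event occurrence" and to "Request the return of any remaining study drug doses". Failure to attend visits is one of the reasons for termination listed there.

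**Analysis.** Section 8.5 opens by assigning vital signs, laboratory measures, weight and similar data to the safety population. A following sentence says that "the treatment-emergent adverse events will be grouped by organ-system and tabulated by treatment assignment", with rates compared by chi-square or Fisher's test. That sentence names no population.

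**SAE definition.** Section 7.5 says that "SAEs will be defined as any adverse experience that is unexpected or: i) results in death", and the list continues to criterion vi. The same section defines an unexpected event by its consistency with the known risk information. Sections 7.9 and 7.11 require an event to be associated with treatment, serious and unexpected.

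**The concern.** A safety set is normally defined by exposure. Here it also depends on attendance after exposure, and attendance can itself be affected by the drug. The starting dose of 500 mg/day is also the lowest permitted dose (5.0, 5.1), and anyone who cannot tolerate it is discontinued. A participant who does badly in the first week therefore has no lower dose to move to, and may leave before visit 3. If that happens more often on active treatment, the exclusion is not neutral between arms. At stake are the by-arm adverse-event rates, which are the main comparative safety output of a small trial.

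The second matter is a reporting definition and does not bear on the analysis set. If *unexpected* alone makes an event serious, a mild event absent from the risk information becomes an SAE. Section 7.8 applies the SAE criteria event by event, so this wording would govern conduct.

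**Working it through.** **1. Can a participant with a recorded event fall outside the set?**
- Drug is dispensed at visit 2 (7.2), so visit 3 is the first additional visit.
- Someone who attends no later visit fails the 8.3 condition.
- That person can still have an event on record, volunteered (7.6) or obtained in a telephone assessment (11.3).
- So the answer is yes. An on-site final assessment might count as coming in, which narrows the group.

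**2. Effect of one lost event.** Input: 33 per arm (8.6), so one participant is 1/33 = 3.0% of an arm. Let p be the rate among the 32 who return, and let the one who does not return have a recorded event.
- As written: p.
- All treated: (32p + 1)/33.
- Difference: (1 − p)/33.

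**3. Cost of the fix.** If the non-returner cannot be reached, there is no event to lose, but that person joins the denominator. The rate goes from p to 32p/33, a dilution of p/33.

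| p | Loss per recorded event, (1 − p)/33 | Dilution per unreachable person, p/33 |
|---|---|---|
| 0% | 3.0 points | 0 points |
| 10% | 2.7 | 0.3 |
| 20% | 2.4 | 0.6 |
| 30% | 2.1 | 0.9 |

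**4. Worked example.** The documents give no event counts or early-loss counts, so these are assumed. Take 5 events among 33 treated, 5/33 = 15.2%.
- One non-returner with an event: 4/32 = 12.5% as written, lower by 2.7 points.
- Two such: 3/31 = 9.7%, lower by 5.5 points.
- One unreachable non-returner and 5 events on record: 5/32 = 15.6% as written and 5/33 = 15.2% after the fix, a dilution of 0.5 points.

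**5. Effect on the test in 8.5** (two-sided Fisher, assumed counts, events lost from the first arm only).

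| All treated | One event lost | Two events lost |
|---|---|---|
| 6/33 v 1/33, p = 0.105 | 5/32 v 1/33, p = 0.105 | 4/31 v 1/33, p = 0.190 |
| 9/33 v 2/33, p = 0.044 | 8/32 v 2/33, p = 0.044 | 7/31 v 2/33, p = 0.078 |

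In these examples one lost event leaves the p-value unchanged to three decimals. Two in the same arm can move it across 0.05.

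**6. SAE wording.** Under 7.5, unexpected implies serious. Substituting this into 7.9 and 7.11, the triple condition (associated, serious, unexpected) reduces to associated and unexpected, so *serious* does no work. A mild, unlisted event would enter the 24- and 48-hour SAE reports of 7.4 and, if associated with the drug, the 15-day FDA report and the 10-day IRB report. Criteria i to vi do not include life-threatening events, although 7.5 defines that term.

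**The case against.** The strongest reply is that 8.5 ties the safety population only to measurements that mostly need a visit anyway, while the adverse-event sentence stands apart and names no population. The loss of events from the tables is therefore inferred. That is correct. However, the sentence follows directly from one about the safety population and no other safety set exists, so this is the natural reading. On the other reading the adverse-event denominator is left unspecified, and the remedy is the same.

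The affected group is also small: dosed, never seen again, reached by telephone or volunteering an event, and having had one. No count is given. This stands, and it limits the point to minor.

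Three stronger readings are tempting and should not be drawn.
- *The exclusion could suppress the 25% notice to the investigators in 7.4.* For example, 9/33 = 27.3% becomes 7/31 = 22.6%. But 7.4 states no denominator and does not mention the safety population, so the documents show neither that the notice is affected nor that it is not.
- *Section 7.5 contradicts 7.9 and 7.11.* It does not. Those conditions still operate, with one of them redundant.
- *Life-threatening events could escape reporting.* Largely not. Sections 7.10 and 7.11 already expedite associated, unexpected life-threatening events without requiring *serious*. What remains is an expected life-threatening event that meets none of i to vi.

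It is also fair to say that the SAE wording has no bearing on 8.3 and adds no weight to it, since 8.5 does not analyse by SAE status.

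**Conclusion.** Both parts hold, and both are minor.

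The attendance condition in 8.3 certainly puts some treated participants outside the safety population. That their recorded events then drop out of the by-arm tables is an inference from 8.5. If it is right, each such event lowers the arm's rate by 2.1 to 3.0 points for p between 30% and 0, assuming 33 treated per arm. The number of such participants is unknown. Differential loss by arm is plausible from the dosing rules, but nothing in the documents demonstrates it. Event recording (7.6), individual SAE reports (7.4), CONSORT withdrawal reasons (8.4) and the efficacy analysis do not depend on the safety population.

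The SAE clause in 7.5 errs towards over-reporting. Its cost is unnecessary expedited reports; participants lose no protection by it.

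**What to change.** **Safety population (8.3, 8.5).**
- Define it as all randomised participants who received study medication, with no later-visit requirement.
- Presume that at least one dose was taken unless there is evidence that none was, such as all capsules returned or a telephone report. The rule is needed because pill counts "will start at visit 3, i.e., post randomization", so someone who never returns has no count.
- State in 8.5 that this set is the denominator for the adverse-event tables and that events reported by telephone are included.
- Report by arm how many participants could not be reached, since they enter the denominator without event data.

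**SAE definition (7.5).** Delete *is unexpected or*, and add *is life-threatening*, as already defined there, to criteria i to vi. A criterion for important medical events is optional. It appears nowhere in the documents and would need an investigator judgement for each event, but it would keep important unexpected events within the SAE reports.

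**Cost.** Wording only, with no new visits or participants. The one statistical downside is the dilution of p/33 per unreachable participant shown above, which the by-arm count makes visible.
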